#### 3.2.2. Rationale for Dose Selection

Previous versions of this protocol randomized patients to receive fixed-dose, subcutaneous (SC) injections of 1 mg of fasinumab Q4W, 3 mg fasinumab Q4W, 6 mg fasinumab Q8W (with alternating placebo injections at the monthly visits where fasinumab will not be given, to maintain the blind), naproxen active comparator, or matching placebo. Based on April 2018 recommendations from the independent DMC for this study that reviewed unblinded data from a different ongoing phase 3 study of fasinumab (R475-PN-1523), the decision was made to discontinue further evaluation of fasinumab at 3 mg Q4W or 6 mg Q8W in the phase 3 program. This recommendation was based on an imbalance in clinically relevant adverse events including time to total joint replacement, peripheral edema, arthralgia and a trend towards fractures. Under amendment 4 global, all patients previously randomized to 3 mg Q4W or 6 mg Q8W under an earlier version of the protocol were discontinued from study drug, but encouraged to otherwise continue all protocol visits and study procedures in the follow-up period and the end of study phone call. Based on the independent DMC review, study of lower dose levels (eg,1 mg Q4W) may continue to be evaluated in the OA population. Given the discontinuation of the 3 mg and 6 mg doses, greater exposure to the fasinumab 1 mg dose is required to increase the size of the fasinumab safety database for potentially clinically relevant doses. Under this amendment, exposure to the fasinumab 1 mg dose will be increased by continuing to enroll patients into the 1 mg Q4W group as planned, and adding a 1 mg Q8W group to increase exposure to the 1 mg dose and to replicate the efficacy profile of this dose regimen, which was first evaluated in R475-PN-1523.

Clinical trial data, including PK data, that support selection of these fasinumab doses include those from the phase 1 studies in healthy volunteers (R475-PN-0817 and TDU-11480), the R475-PN-0901 phase 2 proof-of-concept study in patients with pain due to OA of the knee, the R475-PN-1227 phase 2/3 study in patients with OA of the hip or knee, the R475-PN-0908 single-dose, proof-of concept study in patients with sciatic pain.

Single subcutaneous (SC) doses of fasinumab of up to 30 mg were well-tolerated in healthy male and female subjects in the TDU-11480 study. All single IV doses of fasinumab in the R475-PN-0817 study in healthy male and female subjects were generally well tolerated at all but the highest IV dose (1 mg/kg). The occurrence of neurosensory AEs, which were transient and non-severe, led to the decision to refrain from escalating above the 1 mg/kg IV dose and instead, to expand enrollment of the 1 mg/kg IV cohort.

In the R475-PN-0901 phase 2 proof-of-concept study of fasinumab in patients with pain due to OA of the knee, multiple IV doses of up to 0.3 mg/kg administered Q8W demonstrated efficacy with regard to pain relief and were well tolerated in Caucasian subjects. All 3 doses of fasinumab (0.03 mg/kg, 0.1 mg/kg, and 0.3 mg/kg IV Q8W) were associated with greater improvement compared with placebo in walking index knee pain, standardized total WOMAC score, WOMAC subscales (pain, function, and stiffness) and Patient's Global Impression of Change. However, it was noted that pain relief had the slowest onset with the lowest (0.03 mg/kg) dose.

In the R475-PN-1227 phase 2 study of fasinumab in patients with pain due to OA of the hip or knee, all SC doses (1 mg, 3 mg, 6 mg, and 9 mg Q4W) demonstrated efficacy in pain relief and physical function measures, based upon WOMAC pain and physical function scales assessed after 16 weeks of treatment. Considering the relative lack of an observed dose response for efficacy and increased risk of AA with both the 9 mg and 6 mg Q4W doses, the latter doses are no longer

being studied for the treatment of pain due to OA. Neuromuscular AEs, such as arthralgia and paresthesia, were reported more frequently in fasinumab treated patients than in placebo-treated patients, though these events were typically mild or moderate in intensity. The efficacy and safety data from the 1 mg and 3 mg Q4W dose regimens in R475-PN-1227 supported the previous dose selection of 1 mg and 3 mg Q4W and 6 mg Q8W for the present study. Now, with the removal of the 3 mg Q4W and 6 mg Q8W dose regimens due to emerging safety information, the 1 mg Q4W dose regimen will continue to be evaluated in this study and is deemed to have a favorable benefit-risk profile. The addition of the 1 mg Q8W dose regimen will aid in the determination of a minimally efficacious dose. Note, with this amendment all dose regimens of study drug have been discontinued.

All randomized patients in Year 1 will receive orally administered naproxen (500 mg twice daily) or matching placebo. The 500 mg twice daily naproxen dose is a standard, approved dose for pain associated with OA.

All patients who choose to enter Year 2 will take 500 mg naproxen as needed (ie, prn), which is considered standard-of-care for pain associated with OA, or naproxen-matching placebo prn. The prn dosing schedule was chosen considering the known safety profile associated with chronic NSAID use. In general, the lowest effective dose should be used for the shortest duration taking into consideration the patient's medical history, concomitant medications, comorbidities, and age. The maximum dose allowed will be no more than the amount allowed during Year 1 (ie, 500 mg twice daily).

#### 4. STUDY VARIABLES

## 4.1. Demographic and Baseline Characteristics

Baseline characteristics will include standard demography (eg, age, race, weight, height, etc.), disease characteristics including medical and surgical history, and medication history for each patient.

## 4.2. Primary and Secondary Endpoints

#### 4.2.1. Primary Endpoint

The co-primary endpoints are:

- 1. Change in the WOMAC pain subscale scores from baseline to week 16 in patients treated with fasinumab compared with that of patients treated with placebo.
- 2. Change in the WOMAC physical function subscale scores from baseline to week 16 in patients treated with fasinumab compared with that of patients treated with placebo.

#### 4.2.2. Secondary Endpoints

The key secondary endpoints of the study are:

1. Change in the Patient Global Assessment (PGA) scores from baseline to week 16 in patients treated with fasinumab compared with that of patients treated with placebo

- 2. Percentage of patients treated with fasinumab, compared with that of patients treated with placebo, who had a response at week 16, with response defined as an improvement by ≥30% in the WOMAC pain subscale scores
- 3. Change in WOMAC pain subscale scores from baseline to week 16 in patients treated with fasinumab, compared with that of patients treated with naproxen
- 4. Change in WOMAC physical function subscale scores from baseline to week 16 in patients treated with fasinumab, compared with that of patients treated with naproxen
- 5. Change in WOMAC pain subscale scores from baseline to week 44 in patients treated with fasinumab, compared with that of patients treated with placebo
- 6. Change in WOMAC physical function subscale scores from baseline to week 44 in patients treated with fasinumab, compared with that of patients treated with placebo
- 7. Change in the PGA scores from baseline to week 44 in patients treated with fasinumab compared with that of patients treated with placebo
- 8. Change in the PGA scores from baseline to week 16 in patients treated with fasinumab compared with that of patients treated with naproxen
- 9. Change in WOMAC pain subscale scores from baseline to week 44 in patients treated with fasinumab, compared with that of patients treated with naproxen
- 10. Change in WOMAC physical function subscale scores from baseline to week 44 in patients treated with fasinumab, compared with that of patients treated with naproxen
- 11. Percentage of patients treated with fasinumab, compared with that of patients treated with naproxen, who had a response at week 16, with response defined as an improvement by ≥30% in the WOMAC pain subscale scores
- 12. Change in WOMAC pain subscale scores from baseline to the average score across weeks 4, 8, 12 and 16, in patients treated with fasinumab compared with that of patients treated with placebo
- 13. Change in WOMAC physical function subscale scores from baseline to the average score across weeks 4, 8, 12 and 16, in patients treated with fasinumab compared with that of patients treated with placebo
- 14. Change in WOMAC pain subscale scores from baseline to the average score across weeks 36, 40 and 44 in patients treated with fasinumab compared with that of patients treated with placebo
- 15. Change in WOMAC physical function subscale scores from baseline to the average score across weeks 36, 40 and 44 in patients treated with fasinumab compared with that of patients treated with placebo

#### 4.2.3. Exploratory Endpoints

The exploratory endpoints in the study are:

1. Change from baseline to weeks 16 and 44 in patient-reported outcome measures in patients with pain due to OA of the knee or hip treated with fasinumab compared to placebo

- 2. Change from baseline to weeks 16 and 44 in patient-reported outcome measures in patients with pain due to OA of the knee or hip treated with fasinumab compared to naproxen
- 3. The proportion of patients taking rescue medication, number of days on rescue medication, and weekly average use of rescue medication from baseline to weeks 16 and 44 in patients with pain due to OA of the knee or hip treated with fasinumab compared to placebo
- 4. The proportion of patients taking rescue medication, number of days on rescue medication, and weekly average use of rescue medication from baseline to weeks 16 and 44 in patients with pain due to OA of the knee or hip treated with fasinumab compared to naproxen
- 5. Percentage of patients treated with fasinumab, compared with that of patients treated with placebo, who had improvements of ≥50% and ≥70% in the WOMAC pain subscale scores at weeks 16 and 44
- 6. Percentage of patients treated with fasinumab, compared with that of patients treated with placebo, who had improvements of ≥30%, ≥50% and ≥70% in the WOMAC pain subscale scores at weeks 16 and 44
- 7. Percentage of patients treated with fasinumab, compared with that of patients treated with placebo who met the OMERACT-OARSI criterion at weeks 16 and 44
- 8. Descriptive analyses of the change from baseline at all visits from weeks 52E and 104E of the WOMAC pain and physical function subscale scores in patients with pain due to OA of the knee or hip treated with fasinumab compared to naproxen prn
- 9. Descriptive analyses of the change from baseline at all visits from weeks 52E and 104E in patient-reported outcome measures in patients with pain due to OA of the knee or hip treated with fasinumab compared to naproxen prn
- 10. The proportion of patients taking rescue medication, number of days on rescue medication, and weekly average use of rescue medication from weeks 52E to 104E in patients with pain due to OA of the knee or hip treated with fasinumab compared to placebo
- 11. The proportion of patients taking rescue medication, number of days on rescue medication, and weekly average use of rescue medication from weeks 52E to 104E in patients with pain due to OA of the knee or hip treated with fasinumab compared to naproxen

## 4.3. Safety Endpoints

#### 4.3.1. Safety Endpoints for Year 1 (All Randomized and Treated Patients)

Safety endpoints for Year 1 (through week 52) will include:

- Incidence of AA (as confirmed by independent adjudication)
- Incidence of DA (as confirmed by independent adjudication)
- Incidence of TEAEs
- Incidence of sympathetic nervous system dysfunction (as diagnosed after consultation with an appropriate specialist, such as a neurologist and/or cardiologist)

- Incidence of peripheral sensory AEs that require a neurology or other specialty consultation
- Incidence of all-cause JRs

The incidence of JRs at the telephone survey 52 weeks after the last dose of study drug (week 100) will also be evaluated.

## 4.3.2. Safety Endpoints for Year 2 (All Randomized and Treated Patients Proceeding into Year 2)

The safety endpoints listed above in Section 4.3.1 will be evaluated for Year 2 from the first dose of study drug given in Year 2 through week 104E (end of treatment), as well as for the periods of Year 1 and 2 from day 1 through week 104E.

The incidence of JRs at the telephone survey 52 weeks after the last dose of study drug (week 152E) will also be evaluated.

#### 4.4. Pharmacokinetic Variables

The PK variables will consist of fasinumab concentrations in samples collected at time points specified in Table 1 and Table 2.

## 4.5. Anti-Drug Antibody Variables

Anti-drug antibody (ADA) variables include ADA status (positive or negative), titer, neutralizing antibody (NAb) status, and time point/visit. Samples in this study will be collected at the clinical visits specified in Table 1 and Table 2.

#### 5. STUDY DESIGN

## 5.1. Study Description and Duration

[figure not shown]
This study is a randomized, double-blind, placebo- and naproxen-controlled study designed to evaluate the efficacy and safety of fasinumab in patients with OA of the knee or hip who have a history of inadequate pain relief with acetaminophen/paracetamol and a history of intolerance to or inadequate pain relief from opioids (or are unwilling to take opioids or have lack of access to opioids).

The overall study period for patients in Year 1 who do not participate in Year 2 will be up to approximately 105 weeks including screening and pre-randomization. For these patients, the study consists of a screening period of up to 30 days, a 7 to 10-day pre-randomization/washout period (7 days with a +3 day window), a 52-week treatment period, a 20-week follow-up period, and a final phone call approximately 52 weeks after the last dose of SC study drug (Figure 1). At the end of the Year 1 treatment period, eligible patients can choose to consent to Year 2 and undergo a second year of treatment instead of entering the 20-week follow-up period. Note: As of 26 March 2020, all enrollment into Year 2 has been terminated due to the COVID-19 pandemic. Any patients currently enrolled in Year 2 are to remain in the study. Patients who participate in Year 2 will receive treatment for a total of 104 weeks and will then enter a 20-week follow-up period followed

by the final phone call approximately 52 weeks after the last dose of SC study drug (Figure 1). Note: As of 17 August 2020, all patients on treatment have been permanently discontinued from study drug and will complete the End of Treatment visit. This impacts only patients in the Year 2 treatment period as treatment in Year 1 has ended. All patients will be encouraged to complete all remaining study visits and procedures in the follow-up period and the end of study phone call.

Study weeks during Year 2 will be denoted with an E to represent study weeks during the extension (eg, week 52E) and to differentiate them from study weeks with the same numbers in the follow-up period for patients who only participate in Year 1.

Figure 1: Study Flow Diagram

Abbreviation: EOS- End of study

#### **5.1.1.** Screening and Pre-Randomization

At the screening visit, patients will consent to all study assessments planned for Year 1 and will be informed that they could potentially continue in the study for a second year if they meet eligibility requirements for Year 2. Eligibility and consent for Year 2 will be conducted at the end of Year 1.

Prior to randomization, patients will undergo screening procedures, including X-ray of the shoulders, hips, and knees. Magnetic resonance imaging of the index and contralateral joints must be performed at screening and the results assessed by the central imaging vendor. In addition, an MRI will be performed on any knee or hip joint with a K-L score of ≥3. Randomization visits cannot occur until there is confirmation from the central imaging vendor that there are no exclusionary findings on the X-rays and any required MRIs. During the screening period, all patients will continue to take their current treatment regimen for OA pain, which must include use of an oral NSAID on a regular basis, defined as approximately 4 days per week over the last 4 weeks.

Patients eligible for the study will complete a pre-randomization period, during which all pain medication, except for the study-provided rescue medication (acetaminophen/paracetamol), will be discontinued. The pre-randomization visit will be 7 to 10 days (7 days with a +3 day window) before the randomization visit. Patients will discontinue and/or undergo a washout of, their standard-of-care pain medications for OA during the pre-randomization period. As needed, patients may take acetaminophen/paracetamol for pain relief according to the regional standard-of-care (see Section 7.2 for details). Acetaminophen/paracetamol must not be taken within 24 hours prior to the randomization visit.

#### 5.1.2. Rescreening

#### Re-testing During Screening or Pre-randomization

An assessment that fails to meet eligibility criteria may be repeated once within the screening or pre-randomization period when approved by the Sponsor or designated Medical Monitor under either of the following conditions: 1) the failure is believed by the investigator to be due to a condition that would resolve or could be treated, or 2) a laboratory value minimally exceeds the cut-off value and is not clinically relevant. Only the assessments that did not meet the eligibility criteria require repetition, if done within the screening period or pre-randomization period. Patients may not repeat any assessments if they do not meet the WOMAC criteria or have orthostatic hypotension (defined in Section 8.2.3.4) during the screening or pre-randomization visit.

#### Rescreening Due to Screen Failure

Rescreening can be completed for patients who fail to meet the screening visit window requirements or who are unable to complete all imaging assessments within the specified screening period. Patients who are rescreened after the pre-randomization window must be declared screen failures, be registered in the IVRS as a new patient with a new identification number, and then repeat all screening procedures, with the exception of imaging assessments. Any imaging assessments would need to be repeated only if they were taken more than 60 days from completion of the previous screening X-rays and MRI assessments. Patients cannot rescreen if they have

screen failed due to not meeting the WOMAC criteria or have orthostatic hypotension (defined in Section 8.2.3.4) during the screening or pre-randomization visit.

#### 5.1.3. Randomization

Enrollment of approximately 2845 patients is planned for this study, which includes a total of 285 patients who were enrolled in the fasinumab 3 mg SC Q4W and 6 mg SC Q8W groups under earlier versions of the protocol before dosing was discontinued due to the urgent safety measure, and a total of approximately 2560 patients who will be randomized to fasinumab 1 mg SC Q4W, 1 mg SC Q8W, naproxen, and placebo.

At the baseline visit of Year 1, patients will be randomized 3:3:3:1 to the following treatment groups as follows:

- Fasinumab 1 mg SC Q4W
- Fasinumab 1 mg SC Q8W
- Naproxen 500 mg oral, twice daily
- Placebo

Prior to amendment 5 global, it is estimated that approximately 560 patients were randomized as follows: 240 patients to the fasinumab 1 mg SC Q4W group, 240 patients to the naproxen-only group and 80 patients to the placebo group. Under amendment 5 global, a further 2000 patients were planned to be randomized as follows: 600 patients to the fasinumab 1 mg SC Q4W group, 600 patients to the naproxen-only group, 200 patients to the placebo group, and 600 patients to the newly added fasinumab 1 mg SC Q8W group. Thus, overall, this study will enroll approximately 2560 patients as follows: 840 patients to the fasinumab 1 mg SC Q4W group, 600 patients to the 1 mg SC Q8W group, 840 patients to the naproxen group, and 280 patients to the placebo group.

Prior to amendment 5 global, approximately 285 patients were enrolled in the fasinumab 3 mg SC Q4W and fasinumab 6 mg SC Q8W groups. However, dosing in these patients was discontinued, as recommended by the independent DMC in April 2018.

Patients will receive treatment as described in Section 7.1. Randomization will be stratified according to the affected index joint (hip or knee), the K-L score (2 to 3 or 4) at the screening visit, and geographical region.

Eligible patients who choose to participate in Year 2 will not be re-randomized at week 52. See Section 7.1 for treatment assignments in Year 2.

#### 5.1.4. Treatment Period for Year 1

During the treatment period (day 1 through week 52), patients will be permitted to use only acetaminophen/paracetamol as rescue medication. The study visits during the treatment period will include 1 phone visit on day 8 ( $\pm 1$  day). Patients will record their use of acetaminophen/paracetamol in a diary. Patients should discontinue use of acetaminophen/paracetamol at least 24 hours prior to the start of each study visit in order to minimize the confounding effects of the rescue medication on efficacy measurements.

Efficacy will be assessed by the change from baseline in the WOMAC pain and physical function subscale scores, the PGA, the 36-item Short Form Survey (SF-36), the EuroQoL 5 Dimensions 5 Level Questionnaire (EQ-5D-5L), the Numeric Rating Scale (NRS) of the average walking index joint pain, the Work Productivity and Activity Impairment-Osteoarthritis (WPAI-OA), the Healthcare Resource Utilization (HCRU) questionnaire, and the Treatment Satisfaction Questionnaire for Medication (TSQM). The WOMAC total and stiffness scores will also be evaluated.

Safety assessments will be performed at each study visit during treatment period, as outlined in Table 1.

At the end of the treatment period, patients will either enter the 20-week follow-up period or will be offered by their investigator to enter Year 2, if eligible.

#### 5.1.5. Treatment Period for Year 2

During the treatment period of Year 2 (week 52E through week 104E), patients will be permitted to use only acetaminophen/paracetamol as rescue medication. Patients will record their use of acetaminophen/paracetamol in a diary. Patients should discontinue use of acetaminophen/ paracetamol at least 24 hours prior to the start of each study visit in order to minimize the confounding effects of the rescue medication on efficacy measurements.

Efficacy will be assessed by the change from baseline in the WOMAC pain and physical function subscale scores, the EQ-5D-5L and the WPAI-OA. The WOMAC total and stiffness scores will also be evaluated.

Safety assessments will be performed at each study visit during treatment period, as outlined in Table 2.

#### 5.1.6. Follow-Up Period

At the end of the treatment period (week 52 for patients participating in Year 1 only, or week 104E for patients participating in Year 1 and Year 2), follow-up of patients will continue for an additional 20 weeks. Safety and efficacy assessments will be performed according to the schedule outlined in Table 1 (for patients participating in Year 1 only) or Table 2 (for patients participating in Year 1 and Year 2).

If a patient must undergo JR surgery during the study, he or she will be asked to complete pre-operative imaging and to undergo post-surgery follow-up as outlined in Table 3.

#### **5.1.7. End of Study Phone Contact**

The end of study phone contact will be at week 100 for patients participating in Year 1 only or week 152E for patients participating in Year 1 and Year 2.

A phone contact questionnaire will be conducted at approximately 52 weeks after administration of the last dose of fasinumab or fasinumab-matching placebo to document patient status with regard to JR surgery (if patient underwent, is scheduled for, or is on a wait list for JR surgery). Patients who had an AA will have an MRI performed of the affected joint(s). If the affected joint has undergone JR an X-ray may be substituted for an MRI.

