#### 7.3.2.1. Reasons for Permanent Discontinuation of Study Drug

As of 17 August 2020, all patients in the Year 2 Treatment Period must be immediately discontinued from study drug, undergo all End of Treatment visit assessments, and move directly into the 20-week safety follow-up period.

Prior to 17 August 2020, study drug dosing was to be permanently stopped in the event of any of the following:

- A patient who is currently enrolled under an earlier version of this protocol must be immediately discontinued from study drug, undergo all end of treatment visit assessments, and move directly into the 20-week safety follow-up period under this version of the protocol, if they meet any of the following conditions that were excluded after re-evaluating the safety profile of NSAIDs:
  - They have a known medical history (at any time) of peripheral vascular disease, transient ischemic attack, cerebrovascular accident, myocardial infarction, unstable angina, or documented atherosclerotic cardiovascular disease; or
  - They have a known GFR <30 mL/minute/1.73m^2 or,
  - They are currently taking combination therapy of a diuretic with either an ACE inhibitor or ARB (Note: Patients may remain in the study if they are willing and able to change their antihypertensive regimen such that they are no longer on a combination of a diuretic with either an angiotensin-converting enzyme (ACE) inhibitor or angiotensin receptor blocker (ARB)
- A patient who was randomized under an earlier version of the protocol to 3 mg Q4W or 6 mg Q8W fasinumab
- A patient developing clinically significant peripheral sensory or motor neurologic events confirmed by a neurologist's examination and graded by the neurologist as at

least moderate peripheral neuropathy limiting activities of daily living (ADL), ie, grade ≥2 according to Common Terminology Criteria for Adverse Events (CTCAE) v.4; study sites should use CTCAE v.4 criteria throughout the study for consistency

- Evidence of pregnancy
- A patient developing new or worsening signs and symptoms indicative of carpal tunnel syndrome
- Continued non-compliance with protocol-defined maximum acetaminophen/paracetamol use (with a maximum daily dose of 2500 mg [countries where 500 mg strength tablets / capsules are available] or 2600 mg [countries where 325 mg strength tablets / capsules are available]) during the treatment and follow-up periods, after appropriate counseling

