## **8.2.3.9.** End of Study Phone Contact

An end of study phone contact will be conducted at 52 weeks following the last dose of SC study drug. Patients will be asked whether they underwent JR surgery following the last in-clinic visit of the follow-up period or whether they are scheduled (or on a waiting list) for JR surgery. Patients who had JR surgery will also be asked to submit pre-operative imaging (X-ray and MRI, if available) for adjudication. Patients who had an AA will have an MRI performed of the affected joint(s). If the affected joint has undergone JR an X-ray may be substituted for an MRI.

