## 2. INVESTIGATION PLAN

### 2.1. Study Design and Randomization

The study consists of a screening period of up to 30 days, followed by a 7 to 10-day pre-randomization period. All randomized patients in this study will participate in Year 1, a 52-week randomized, double-blind, placebo- and naproxen-controlled treatment period. At the end of the 52-week treatment period, eligible patients have the option to continue for another 52-week double-blind naproxen-controlled treatment period called Year 2, followed by a 20-week follow-up period. Patients who do not consent, or are ineligible, for Year 2 will continue in a 20-week follow-up period. Patients are contacted by phone approximately 52 weeks after their last subcutaneous (SC) dose of study drug (Figure 1).

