##### All-cause Joint Replacements

The number and percentage of patients with all-cause joint replacements will be presented by treatment group for the, Treatment and Follow-up Periods both Year 1 and Year 2. The number of replacements in joints that were positively adjudicated will be summarized by treatment

group. Joint replacements will also be summarized by KL score of the affected joint at screening.

The time to JR is calculated as:

$$= (\text{Date of JR} - \text{Date of first dose of study drug in Year 1}) + 1$$

Plots of the Kaplan Meier curves by treatment group (as randomized to in Year 1) of time to JR will be presented based on the SAF – Year 1. Patients without an event will be censored at the last contact.

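### The final joint-replacement call has two timings that separate once injections stop early, and nothing says which governs

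*Protocol*

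**What the plan says.** Protocol 5.1.7 gives two rules in consecutive paragraphs. The first is a fixed week: "The end of study phone contact will be at week 100 for patients participating in Year 1 only or week 152E" for those who continue into Year 2. The second is tied to dosing: "A phone contact questionnaire will be conducted at approximately 52 weeks after administration of the last dose of fasinumab or fasinumab-matching placebo".

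Other sections take one side or the other:

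- **Fixed week.** The Schedule of Events sets Day 701 ±7 (Table 1) and Day 1065E ±7 (Table 2).
- **Dose anchor.** Protocol 8.2.3.9: "An end of study phone contact will be conducted at 52 weeks following the last dose of SC study drug". SAP 2.1: "Patients are contacted by phone approximately 52 weeks after their last subcutaneous (SC) dose of study drug". The synopsis, 5.1 and 9.6.1.4 agree with these.
- **Both at once.** Section 4.3.1: "The incidence of JRs at the telephone survey 52 weeks after the last dose of study drug (week 100) will also be evaluated". Section 4.3.2 does the same with week 152E.

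What happens after early stopping also varies. The synopsis (Study Duration), 7.3.2 and footnote 1 to Table 1 keep most patients who stop drug on the visit schedule. Section 7.3.2 says so specifically for stops due to adjudicated arthropathy (AA). Sections 7.1 and 7.3.2.1 send other patients straight into the 20-week follow-up: the former 3 mg and 6 mg groups, patients with newly excluded conditions, and the Year 2 patients covered by "As of 17 August 2020, all patients in the Year 2 Treatment Period must be immediately discontinued from study drug".

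In the SAP (5.8.7, All-cause Joint Replacements), time to replacement runs from the first Year 1 dose, with Kaplan-Meier curves by randomised group. "Patients without an event will be censored at the last contact".

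**The concern.** All-cause joint replacement is a listed safety endpoint, and its incidence at this call is evaluated separately. Protocol 1.2 reports a higher chance of joint replacement in fasinumab-treated patients who develop joint damage, and AA requires permanent discontinuation of study drug (7.3.2.1).

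If the call follows the last dose, patients who stop early are last asked about surgery sooner after first dose than patients who complete dosing. An incidence labelled week 100 would then mix different lengths of follow-up. Time-to-event censoring would also depend on when, and partly why, dosing stopped. Sites reading different sections could apply different rules to similar patients.

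**Working it through.** **Inputs.** SC injections are every 4 weeks from Day 1, 13 in Year 1 (Protocol 6.2.3 and Table 1), so the last planned one is at week 48. In Year 2 it is at week 100E, Day 701E (Table 2). The dose anchor is 52 weeks = 364 days. The last scheduled Year 1 clinic visit is week 72.

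**Step 1: reproduce the plan's weeks.** Week 48 is Day 1 + 7×48 = 337, and 337 + 364 = 701, which is week 100. In Year 2, 701 + 364 = 1065, which is week 152E. Both stated times reproduce exactly for a patient who received the last planned injection.

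**Step 2: gap between the rules.** For a last injection at week t, the gap is 100 − (t + 52) = 48 − t weeks in Year 1 and 152 − (t + 52) = 100 − t weeks in Year 2. It runs from 4 weeks (t = 44 or 96E) to 48 weeks (t = 0 or 52E). The smallest gap, 28 days, exceeds the 7-day tolerance.

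**Step 3: observation lost if the dose anchor is used (Year 1).** A patient who stays on schedule and attends week 72 is observed to max(72, t + 52). A patient sent straight to follow-up is observed to t + 52.

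| Last injection (week) | Dose-anchored call (week) | Gap between calls = shortfall if sent straight to follow-up | On schedule: observed to week | On schedule: shortfall against week 100 |
|---|---|---|---|---|
| 0 | 52 | 48 | 72 | 28 |
| 12 | 64 | 36 | 72 | 28 |
| 20 | 72 | 28 | 72 | 28 |
| 24 | 76 | 24 | 76 | 24 |
| 36 | 88 | 12 | 88 | 12 |
| 44 | 96 | 4 | 96 | 4 |
| 48 | 100 | 0 | 100 | 0 |

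**Step 4: internal signs that early stopping was not considered.** Section 8.2.3.9 has the caller ask "whether they underwent JR surgery following the last in-clinic visit of the follow-up period". For an on-schedule patient last injected at week 16 or earlier, the dose-anchored call is at week 68 or earlier (16 + 52 = 68), before the week 72 visit. The SAP's analysis window for this call (6.5, Table 1) opens at Day 604. A dose-anchored call after a week 32 injection falls on Day 1 + 7×32 + 364 = 589, before that window opens.

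**Step 5: Year 2.** Entry closed on 26 March 2020 and dosing stopped on 17 August 2020: 144 days, or 20.6 weeks. The newest entrants were at about 52 + 20.6 = week 72.6E, with a last scheduled injection at about 72E. Their call falls at 72 + 52 = about 124E under one rule and 152E under the other, a difference of 28 weeks.

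**Step 6: illustration of average effect.** The documents do not give the distribution of stopping times. Assume last injections spread evenly over weeks 0, 4, …, 44. The mean gap is (48 + 44 + … + 4)/12 = 312/12 = 26 weeks. The mean on-schedule shortfall is (6×28 + 24 + 20 + 16 + 12 + 8 + 4)/12 = 252/12 = 21 weeks. If 10% to 40% stop early, average follow-up per patient falls by 2.1 to 8.4 weeks if all stay on schedule, and by 2.6 to 10.4 weeks if all are sent straight to follow-up.

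**The case against.** The strongest reply is that the schedule already settles the matter for the patients who matter most. Sections 7.3.2 and 9.6.1.1 direct AA stoppers to the remaining scheduled visits, the synopsis asks stoppers to complete phone contacts as well, and Table 1 puts the call at Day 701. On that reading they lose nothing. This stands to the extent that a reader might infer that AA patients do have the shortest follow-up and are censored early, and the documents do not show that. It happens only if sites follow the dose anchor. But 8.2.3.9, which describes how the call is made, states the dose anchor without exception.

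Other points, and what stands of each:

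- **The call is not the only source of joint-replacement data.** Correct. Clinic visits run to week 72, and surgery triggers its own reporting and visits. So the 36-week gap between calls for a last injection at week 12 should not be read as 36 weeks lost; on schedule the loss is 28.
- **Not everyone who stops early is affected.** Correct. A patient who stops after the week 48 or 100E injection, or stops only the oral drug, has no gap.
- **The August 2020 stop is not risk-related censoring.** Correct. It applied on one date to every patient still on treatment, in all arms. It creates the timing ambiguity but is administrative.
- **Kaplan-Meier estimation handles unequal follow-up.** Only if censoring is unrelated to replacement risk, which is doubtful after a stop for AA or adverse events. Crude incidence at the call has no such protection.
- **Equal follow-up after last exposure is a legitimate safety design.** It is, but it does not match an endpoint labelled week 100 or an analysis timed from first dose.
- **A week 100 call does not satisfy both rules as written.** Correct. Section 8.2.3.9 does not say at least 52 weeks. Even for completers, the windows allow a last dose on Day 344 (344 + 364 = 708) and a call on Day 694. The wording must change.

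**Conclusion.** The contradiction is in the text and does not depend on any assumption. The two timings agree only for a last injection at week 48 or 100E, differ by 4 to 48 weeks otherwise, and no section ranks them.

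The consequence is conditional. If the dose anchor is used, the shortfall against week 100 is at most 28 weeks for a patient who stays on schedule and attends week 72, and up to 48 weeks for a patient sent straight to follow-up. The 3 mg and 6 mg patients are outside the Year 1 safety set (SAP 3.4). In the Kaplan-Meier analysis, the up-to-48-week Year 1 case therefore concerns patients removed for newly excluded conditions. For Year 2 patients not yet dosed at 100E when dosing ended, the difference is about 28 weeks for the newest entrants and less for those further along. These figures use nominal visit weeks and assume no missed injections before the stop.

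The documents do not establish that any group was in fact followed for less time, or the direction of any bias between arms. They leave the joint-replacement incidence at the call without a defined time from first dose. No efficacy, sample-size or power figure is affected.

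**What to change.** Reconcile Protocol 4.3.1, 4.3.2, 5.1.7, 8.2.3.9, 9.6.1.4 and SAP 2.1, with the matching synopsis and 5.1 text, so that:

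1. Joint-replacement status, with the date of any surgery, is ascertained by phone at scheduled week 100 (Year 1 only) or week 152E (Year 2), counted from Day 1, whenever dosing stopped.
2. Patients already called earlier get one further phone status check at that week or, if it has passed, as soon as possible. The surgery date then allows events to be placed correctly in time.
3. Joint-replacement incidence is reported as the Kaplan-Meier estimate at a stated fixed time from first dose, in place of crude incidence at the call.

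The MRI for AA patients is tied to the same contact (5.1.7, 8.2.3.9), so its timing is equally ambiguous. The sponsor must reconcile that separately; nothing is proposed for it here.

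The cost is a short amendment, some later or second phone calls, and a possibly later end of study, by up to about 28 weeks for the newest Year 2 entrants.
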